Methods: We will recruit up to 30 patients with body mass index ≥ 25 kg/m² and prediabetes (defined as hemoglobin A1c [A1c] 5.7-6.4%) from the Ann Arbor VA primary care clinic. Participants will be identified by chart review and invited to participate by postal letter. Individuals that do not opt-out of study contact will be screened for eligibility by telephone call. Interested and eligible participants will be invited to attend an in-person information session. During this session, they will receive information about the dietary intervention; written informed consent will be obtained at this time. Study participants will attend a total of 24 group-based classes over the course of 1-year (not including initial information session). Body weight will be measured at each session. At baseline, 6-months, and 12-months, we will measure waist circumference, A1c, lipid levels, and self-reported outcomes including quality of life, mood, hunger, cravings, physical symptoms, and medication use/changes. Primary outcomes will be feasibility (e.g., enrollment, retention) and acceptability (e.g., session attendance, qualitative feedback). Secondary outcomes will change in weight, achievement of $\geq 5\%$ body weight loss, change in A1c, and change in lipid levels. During semi-structured interviews conducted at 6-months and 12-months, we will explore participants' experiences with the program, barriers to and facilitators of adherence to a low-carbohydrate diet, and perspectives on ways to improve the intervention.

Impact/Implications: Through this study, we will demonstrate the feasibility and acceptability of a LC-DPP among Veterans with prediabetes. These data will inform a large-scale comparative effectiveness trial of LC-DPP versus VA-MOVE.

List of Abbreviations

LC-DPP – low-carb Diabetes Prevention Program

A1c – hemoglobin A1c

Contents

Protocol Title:5

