3.0 Objectives

In this mixed methods pilot study, we aim to test whether a LC-DPP is feasible to deliver in the VA Health System. We hypothesize a LC-DPP will lead to greater participation and weight loss than VA MOVE! In addition to objective measures of this program's preliminary efficacy (e.g. weight, HbA1c) we will also obtain qualitative participant feedback on the intervention. Taken together, these data will be used to improve the curriculum and inform larger-scale interventions.

Aim 1: To evaluate acceptability and feasibility of delivering a Low-Carb Diabetes Prevention Program in the VA Health System

The VA Health System has an established infrastructure to deliver group-based lifestyle programs including VA MOVE! We will deliver a VA LC-DPP that was piloted at a Michigan Medicine primary care clinic in 2017. We will collect data on participant recruitment, session attendance, and intervention satisfaction to assess the acceptability of a VA LC-DPP. Qualitative feedback from VA diabetes educators, primary care providers and LC-DPP participants will be collected to better understand barriers and facilitators of a VA LC-DPP and identify challenges to scalability.

Aim 2: To estimate weight loss from a Diabetes Prevention Program that is modified to incorporate a Low Carbohydrate (LC-DPP) rather than the traditional low fat diet among veterans with prediabetes. We will conduct a single-arm mixed methods pilot study to estimate weight loss as well as the percentage of participants who achieve 5% weight loss in a 16-week LC-DPP. Weight loss from the pilot LC-DPP cohort will be compared to weight loss

outcomes from previously published VA DPP and VA MOVE! studies. We will also evaluate secondary outcomes including change in physical activity, neuropathy symptoms, hemoglobin A1c, triglycerides, cholesterol and HDL over the 12- month study period.

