5.0 Study Procedures

5.1 Study Design

We will conduct a single-arm mixed methods pilot study to test the preliminary efficacy on weight loss of a LC-DPP among Veterans with prediabetes (as defined by the American Diabetes Association [ADA] ²⁴). We hypothesize that at least 50% of LC-DPP participants will achieve at least 5% weight loss at 12 months and that the average weight loss in the LC-DPP will be greater than the average weight loss among historical controls in VA MOVE!.¹¹

Our team previously adapted the Centers for Disease Control and Prevention's (CDC's) National Diabetes Prevention Program (NDPP) curriculum—a lifestyle change program similar to MOVE!—to teach participants to follow a low-carbohydrate rather than a low-fat diet. We pilot tested our low-carbohydrate Diabetes Prevention Program (LC-DPP) among adults with prediabetes at a single, academic medicine primary care clinic.

The LC-DPP curriculum was adapted from the CDC National Diabetes Prevention Program materials and consists of 16 weekly one-hour group sessions over first 6 months (i.e. core phase) and 8 one-hour group sessions once or twice a month over the next 6 months (i.e. maintenance phase). Importantly, our adapted curriculum will adhere to the CDC's Diabetes Prevention Recognition Program (DPRP) guidelines, which aim to maintain the integrity of the DPP in heterogeneous settings. The DPRP formally recognizes sites that achieve specific targets (e.g. session attendance, weight loss) through use of a CDC-approved curriculum. Therefore, our curriculum, if effective, may be eligible for CDC-approval, which would facilitate future dissemination of this intervention.

We will use a mixed-methods sequential explanatory design, which is to say that quantitative data and qualitative data will be collected in two consecutive phases within the study ²⁵. Specifically, in the first phase, we will collect and analyze the quantitative data (e.g. surveys, weight, A1c, lipids). In the second phase, we will collect and analyze qualitative data (e.g. semi-structured interviews). The rationale for this approach is that the quantitative data will provide a general overview of the intervention's efficacy and limitations, and the qualitative data will help to explain these findings by exploring participants' experiences and perspectives in more depth.

Intervention

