Change in body weight: Body weight will be measured and recorded at each attended session. We will calculate average body weight change and percent body weight loss at the end of the program's core phase (6 months) and maintenance phase (12 months). Among session non-attendees, we will attempt to schedule 6- and 12-month weigh-ins at participants' convenience within 2 weeks of the final core and maintenance sessions. All weights will be obtained using the same calibrated scale.

Change in HbA1c: We will calculate change in HbA1c from baseline to 6 and 12 months

Change in lipids: We will calculate change in triglycerides and total cholesterol/HDL ratio from baseline to 6 months and 12 months.

Change in survey measures: We will calculate change in self-reported survey measures from baseline to 6 months and 12 months.

Fidelity: We will measure intervention fidelity (i.e., extent to which components of an intervention are delivered as intended) using quantitative measures adapted from the literature²⁶ as well as qualitative interview feedback from participants and dietitians.

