5.6 Data Analysis

Quantitative analysis

Descriptive statistics will be used for baseline survey response data including demographic and socioeconomic characteristics. For all continuous outcomes, we will calculate mean change and standard deviation from baseline to 6 months and 12 months and compare outcomes from baseline to 6 months and 12 months using paired *t*-tests. For all categorical outcomes, we will

use chi-square or Fisher's exact tests to examine changes from baseline to 6 and 12 months. All analyses will be conducted using Stata 14.

Qualitative analysis:

Semi-structured interviews will be recorded and transcribed verbatim. Interviews will then be imported into qualitative analysis software. Two investigators will independently read and code transcribed interviews. Interviews will then be coded jointly using consensus conferences. Interviews will be analyzed using directed content analysis²⁷, which is to say that codes will be created to reflect the main topics in the interview guide and to characterize the patterns and themes that emerged from the data.²⁸

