Low-Carbohydrate Diabetes
Prevention Program Among
Veterans With Prediabetes (VA LC-
DPP)

Prepared for ClinicalTrials
Resubmission 4/20/21

Statistical Analysis Plan:

Quantitative analysis

Descriptive statistics will be used for baseline survey response data including demographic and socioeconomic characteristics. For all continuous outcomes, we will calculate mean change and standard deviation from baseline to 6 months and 12 months and compare outcomes from baseline to 6 months and 12 months using paired t-tests. For all categorical outcomes, we will use chi-square or Fisher's exact tests to examine changes from baseline to 6 and 12 months. All analyses will be conducted using Stata 14.

Qualitative analysis:

Semi-structured interviews will be recorded and transcribed verbatim. Interviews will then be imported into qualitative analysis software. Two investigators will independently read and code transcribed interviews. Interviews will then be coded jointly using consensus conferences. Interviews will be analyzed using directed content analysis²⁷, which is to say that codes will be created to reflect the main topics in the interview guide and to characterize the patterns and themes that emerged from the data.²⁸

**Cravings:
Control of Eating Questionnaire**

Over the past 7 days...

How strong was your desire to eat sweet foods?	Q1	Answer choices on a sliding scale from 0 to 100 with anchors at 0 and 100:	Items on the CoEQ are assessed by 100 mm VAS with items relating to each subscale being averaged to create	Dalton M, Finlayson G, Hill A, Blundell J. Preliminary validation and principal components analysis of the Control of
How strong was your desire for non-	Q2	0- not at all strong 10 20	to create	

Over the past 7 days, how often have you had cravings for

Sweet foods like	Q3	Answer choices	
Other sweet foods (cakes, pastries, cookies, etc)?	Q4	on a sliding scale from 0 to 100 with anchors at 0 and 100:	
Fruit or fruit juice?	Q5	0- not at all	
Dairy foods (cheese, yogurts, milk, etc)?	Q6	10 20 30 40 50 60 70 80 90 100-	
Starchy Foods that are not sweet like French fries, potato chips,	Q7 Q8	70 80 90 100- extremely often	

Stress Eating

Please indicate how you usually experience a stressful event

I eat more of my favorite foods to	Q1	Answer choices 1 through 4 with anchors on 1 and 4:	Reverse code and sum, so that higher scores indicated	Tsenkova, V., Boylan, J. M., & Ryff, C. (2013). Stress
------------------------------------	----	---	---	--

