Below is a list of reasons that people sometimes give for eating tasty foods and drinks such as:

- Sweets like chocolate, doughnuts, cookies, cake, candy, ice cream, other desserts.
- Salty snacks like chips, pretzels, and crackers.
- Fast foods like hamburgers, cheeseburgers, pizza, fried chicken and French fries.
- Sugary drinks like soda, sweet tea, milkshakes, and smoothies.

To forget y	Q3	1 =	Coping	Burgess,
Because it	Q4	Almost	score:	E. E.,
To cheer u	Q5	never/Ne	Average	Turan, B.,
To forget a	Q6	ver	of four	Lokken, K.
		2 = Some	responses	L., Morse,
		of the	.	A.. &

Energy Levels between Meals

In the past week, two hours after you ate BREAKFAST, how do you feel?

Alert	Q1	Answer	NA	NA
Energetic	Q2	choices 1		
Tired	Q3	through		
Brain fog o	Q4	7, with		
Food cravii	Q5	anchors		
Hunger	Q6	on 1, 7:		
Moodiness	Q7	1- Not at		
		all		
		7		

In the past week, two hours after you ate LUNCH, how do you feel?

Alert	Q8	Answer	NA	NA
Energetic	Q9	choices 1		
Tired	Q10	through		
Brain fod o	Q11	7, with		
Food cravii	Q12	anchors		
Hunger	Q13	on 1, 7:		
Moodiness	Q14	1- Not at		
		all		

Physical Symptoms

How often have you experienced the following over the past week?

Acne	Q1		NA	NA
Bad breath	Q2			
Bloating or	Q3			

Cold hands Q4
Constipation Q5
Diarrhea Q6
Dizziness Q7
Dry mouth Q8
Constant tiredness Q9
Food intolerance Q10

Headaches Q11

Heart palpitations or a racing heart Q12

Heartburn Q13

Joint or muscle pain Q14

Muscle cramps Q15

Nausea Q16

Trouble concentrating Q17

Weakness Q18

Hair loss Q19

Sexual problems Q20

Numbness (loss of sensation) in the feet, legs, or hands Q21

Tingling or prickling sensation in the feet, legs, or hands Q22

Not at all
1 day a week
2-3 days a week
4-5 days a week
6-7 days a week

Burning or shooting pain in the feet, legs, or hands

Q23

Blurred or deteriorating vision

Q24

Please describe any other psychological or physical symptoms that you experienced during the past month.

Q25

Participants may enter free text of whatever they choose.

Health
Global Health PROMIS Questionnaire:

Please respond to each item by marking one box per row

In	Q1	5-	Re-code:	PROMIS
In	Q2	Excellent	Q7 (pain	Health
general,		4- Very	on	Organizati
would		good	average):	on and
you say		3- Good	0 = 5	PROMIS
your		2- Fair	1,2,3 = 4	Cooperati
quality of		1- Poor	4,5,6 = 3	ve Group,
life is:			7,8,9 = 2	2008-
In	Q3		10 = 1	2012.
general,				https://w
how			Global	ww.iconq
would			Physical	uerms.org
you rate			Health	/sites/all/

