5
6
7- you must include them, they were very helpful

Do you have any suggestions about how we can improve the handouts? Which were your favorite or least favorite topics?

Q7

Participants may enter free text of whatever they choose.

Social Support

How often in the last 30 days has your family or friends

Encourage	Q1	1 =	Average	Norman,
Discuss	Q2	Almost	responses	G. J.,
Remind	Q3	never	of the 6	Carlson, J.
you to		2 = Once	questions.	A., Sallis,
choose		in a while	**NOTE:	J. F.,
healthy		3 =	this just	Wagner,
foods.		Sometime	appears	N., Calfas,
Share	Q4	s	to be how	K. J., &
ideas on		4 = Often	it is in the	Patrick, K.
healthy		5 =	scoring,	(2010).
eating.		Almost	but	Reliability
Eat	Q5	always	doesn't	and
healthy			actually	validity of
meals			say how	brief
with you.			to do it.	psychosoc
Complain	Q6			ial
about				measures
eating				related to
healthy				dietary
foods.				behaviors.

Open Ended Support

Have you gotten any feedback from family, friends, or physicians /healthcare providers about this program or your experience with it? If so, what did they say?
	
Q1
	
Participants may enter free text of whatever they choose.
	
NA
	
NA

--	-----------	---	-----------	-----------

Medication Changes

6- month question

Did any of your medications or doses change since starting this program?
	
Q1
	
Yes/No

If yes, please specify which medications were changed or added.
		
Free text

If yes,	Q2	Increased
was the		Decrease
dose		d
increased		I don't
or		know
decreased		
?		

12-month question

Did any of your medications or doses change over the past 6 months program (i.e. maintenance phase)?	Q1	Yes/No
If yes, please specify which medications were changed or added.		Free text
If yes,	Q2	Increased
was the		Decrease
dose		d
increased		I don't
or		know
decreased		
?		

Diet Evaluation

How much do	Q1	Answer choices 1-	NA	NA
-------------	----	-------------------	----	----

How much do you think this diet has improved your physical health? Q2 7 with anchors 1,7: 1- Not at all 2 3 4 5

How much do you think this diet has Q3 6 7- Very much so

How hard is it to stay on your diet? Q4 Answer choices 1-7 with anchors 1,7: 1- Very easy 2

How often do you cheat on your diet? Q5 Answer choices 1-7 with anchors 1,7: 1- Not at all 2 3 4 5 6 7- Very often

Open Ended Diet

When you Q1
follow
this low-
carbohydr
ate food
plan:
What
about
your
health got
better?

Participa NA NA
nts may
enter free
text of

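### Before-after change in categorical outcomes is to be tested with chi-square or Fisher's exact tests, which ignore that both answers come from the same participants

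*SAP*

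**What the plan says.** The SAP's quantitative analysis paragraph gives one rule for each type of outcome. Continuous outcomes get the mean change and a paired t-test. For all categorical outcomes, "we will use chi-square or Fisher's exact tests to examine changes from baseline to 6 and 12 months". Protocol narrative section 5.6 carries the same text: "use chi-square or Fisher's exact tests to examine changes from baseline to 6 and 12 months".

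The outcomes that might fall under the categorical rule are spread over several places:

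- The narrative abstract lists "self-reported outcomes including quality of life, mood, hunger, cravings, physical symptoms, and medication use/changes" among the measures taken at baseline, 6 and 12 months.
- Section 3.0, Aim 2, names "secondary outcomes including change in physical activity, neuropathy symptoms, hemoglobin A1c, triglycerides, cholesterol and HDL".
- Section 5.5 says "We will calculate change in self-reported survey measures from baseline to 6 months and 12 months", without saying which measures are scores and which are categories.
- The SAP's Physical Symptoms block has 24 items, each with five frequency bands and no scoring rule. Neuropathy is covered by Q21 to Q23, for example "Tingling or prickling sensation in the feet, legs, or hands".
- The SAP's Medication Changes block asks "Did any of your medications or doses change since starting this program" at 6 months, with a matching question at 12 months. It has no baseline version.
- Section 5.1 states "We hypothesize that at least 50% of LC-DPP participants will achieve at least 5% weight loss at 12 months". This is the only secondary outcome named that is categorical by definition.

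**The concern.** With one arm, every comparison of baseline with follow-up is within person. Chi-square and Fisher's exact tests treat the two columns of a table as independent groups. The plan respects pairing for continuous outcomes and drops it for categorical ones.

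The rule can be carried out in two ways, and neither gives a suitable test. If the two time points are stacked as two groups, the standard error omits the covariance between a person's answers. With positive correlation the test rejects too rarely and real changes are missed. If baseline is cross-tabulated against follow-up, a layout the plan does not describe, the test is of association between the two answers and not of change. For ordered items, chi-square also ignores the order of the categories, which is a separate loss.

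At stake are the symptom findings of a pilot meant to inform a larger comparative trial. No primary outcome or decision rule depends on them.

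**Working it through.** The plan gives no alpha, power, prevalence or correlation for these outcomes, so it has no figure to reproduce. The figures below are illustrations under stated assumptions.

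**Inputs.** From the protocol: n = 30, the maximum (section 5.1), and n = 22, which is 10% × 220 letters (section 5.2), before attrition. Assumed: two-sided 0.05; prevalence falling from p1 to p2; within-person correlation φ from 0 to 0.5.

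**Paired cell probabilities.** P(yes, yes) = p1·p2 + φ√[p1(1−p1)p2(1−p2)]. For 50% to 25% and φ = 0.5 this is 0.125 + 0.5 × 0.2165 = 0.233. Then b (resolved) = 0.500 − 0.233 = 0.267, and c (new) = 0.250 − 0.233 = 0.017.

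**Power**, by exact enumeration of all paired 2×2 tables:

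| Change | n | φ | Stacked Fisher | Stacked chi-square | Exact McNemar | Mid-p McNemar | Asymptotic McNemar |
|---|---|---|---|---|---|---|---|
| 50% to 25% | 30 | 0.5 | 37% | 52% | 70% | 81% | 83% |
| 50% to 25% | 22 | 0.5 | 21% | 35% | 45% | 61% | 70% |
| 50% to 25% | 22 | 0.3 | 25% | 37% | 36% | 48% | 50% |
| 50% to 25% | 22 | 0 | 29% | 39% | 27% | 36% | 36% |
| 30% to 15% | 22 | 0.3 | 10% | 18% | 12% | 21% | 27% |
| 20% to 10% | 22 | 0.5 | 3% | 8% | 3% | 8% | 18% |

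**Rejection when nothing changes** (prevalence 50, 30 or 20%; φ 0.3 to 0.5; both n): stacked Fisher 0.2–0.8%, stacked chi-square 0.6–2.1%, exact McNemar 0.3–2.3%, mid-p 1.3–4.2%, asymptotic McNemar 3.9–4.9%. The stacked tests fall well short of the nominal 5%.

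**95% interval half-width**, 50% to 25%, φ = 0.5:

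- Unpaired: 1.96√{[p1(1−p1) + p2(1−p2)]/n} = 1.96√(0.4375/30) = 23.7 points; at n = 22, 27.6.
- Paired: 1.96√{[b + c − (b − c)²]/n} = 1.96√(0.221/30) = 16.8 points; at n = 22, 19.6.

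Over the three changes in the table, at φ 0.3 to 0.5, the paired interval is 16–29% narrower.

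**Worked example**, n = 30: 15 report a symptom at baseline and 9 at follow-up, with 6 resolved and none new. Stacked Fisher p = 0.19; stacked chi-square p = 0.11; exact McNemar p = 0.031.

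**Cross-tabulated layout** (hypothetical). With cells 12/3/3/12 there is no net change, yet Fisher gives p = 0.003; exact McNemar gives p = 1. At n = 22, φ 0.3 to 0.5 and no change, Fisher on this table is significant 19–54% of the time.

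**Five-level items.** Simulated from a latent bivariate normal with correlation 0.5 and a shift of 0.6 SD, n = 22:

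| Baseline distribution (%) | 2×5 chi-square | Unpaired Mann-Whitney | Stuart-Maxwell | Wilcoxon signed-rank |
|---|---|---|---|---|
| 40/20/20/10/10 | 16% | 38% | 20% | 57% |
| 75/10/7/5/3 | 4% | 22% | 3% | 29% |

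Taking order into account first recovers 38 − 16 = 22 of the 41 points between chi-square and Wilcoxon in the first row, and 22 − 4 = 18 of 25 in the second. Adding pairing then gives a further 19 and 7 points. Pairing without order adds 4 points and none. Wilcoxon here uses the normal approximation; the exact version gives 54% and 19%.

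**At least 5% weight loss.** Everyone is at zero at baseline by definition, so a before-after test only asks whether anyone lost weight. Fisher against 0/22 reaches p = 0.048 at 5/22 (23%), which says nothing about the 50% hypothesis. Exact (Clopper-Pearson) 95% intervals around 50% are 31–69% at 15/30 and 28–72% at 11/22.

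**The case against.** The strongest objection is reach. Most repeated instruments in the SAP have a numeric score: cravings, stress eating, PROMIS, social support, self-regulation, physical activity, fatigue and sleep. Those fall under the paired t-test. No yes/no item is clearly repeated from baseline, so the binary figures apply only if symptoms are dichotomised, which no section plans. What remains is chiefly the symptom block, and section 5.5 could be read as scoring that too. This stands. It limits the effect on results but does not make the stated rule right, and it leaves the choice open until after the data are seen.

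Second, for five-level items order matters at least as much as pairing, and the split depends on which is taken first. That also stands. Pairing on top of order still adds 19 and 7 points, and the remedy must use both.

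Third, asymptotic McNemar keeps close to the nominal level and has more power than the exact or mid-p versions in most of these cases, so the small gain of exact McNemar for uncommon items partly reflects that version's conservatism. This is fair. Which valid version to use is a choice; the plan needs to name one.

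Fourth, the likely error is conservative, in a pilot whose primary outcomes are unaffected. That is true and is why the grade is low. Reading chi-square as McNemar's chi-square is strained next to Fisher's exact test, and the text would still need correcting.

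**Conclusion.** The concern holds. As written, the rule names unpaired tests for paired data in both documents, and no paired alternative appears.

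For common binary items with well-correlated answers the loss is large: 52% against 81% power at n = 30 (chi-square against mid-p McNemar), and an interval about 29% narrower when paired. At low correlation, or for uncommon items at n = 22, exact McNemar adds little or nothing to the power of chi-square. For ordered items, ignoring category order accounts for about half or more of the loss when order is taken first.

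All sizes rest on assumed prevalence, correlation, shift and a two-sided 0.05, and on items being analysed as categories, which the documents do not settle. Primary outcomes and outcomes tested by paired t-test are untouched. Stacking does not inflate false positives when answers are positively correlated. This should be fixed, at the low end of that grade.

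**What to change.** Change the SAP's quantitative analysis paragraph and protocol section 5.6 in the same way:

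1. List which survey items are analysed as categories and which as scores. Include the symptom items, and Q21 to Q23 in particular, since neuropathy symptoms are a named secondary outcome.
2. Replace the chi-square and Fisher's exact rule. For binary items, use McNemar's test in one named version (mid-p, or exact with a note on its low power at this sample size), with the paired difference in proportions and its 95% interval. For ordinal items, use the Wilcoxon signed-rank test or another paired test that uses category order, rather than a nominal Stuart-Maxwell test. Use participants with both time points.
3. Report at least 5% weight loss as a proportion with an exact 95% interval and no before-after test. The medication-change item has no baseline value either, so no before-after test applies to it; a proportion with an exact interval suits it too.

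The cost is two or three sentences and a short list of items, repeated in section 5.6. No new data are needed.
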